**Statistical Analysis Plan**

**Version: 3**

Lexicon Pharmaceuticals Protocol No. EFC14835

**Date of Issue: 19 February 2020**

Covance Study ID:000000154257

Urinary tract infections	10051350	Cytomegalovirus urinary tract infection
Urinary tract infections	10051959	Urinary bladder abscess
Urinary tract infections	10052238	Escherichia urinary tract infection
Urinary tract infections	10054088	Urinary tract infection bacterial
Urinary tract infections	10056351	Emphysematous cystitis
Urinary tract infections	10058523	Bladder candidiasis
Urinary tract infections	10058596	Renal cyst infection
Urinary tract infections	10059517	Bacterial pyelonephritis
Urinary tract infections	10061181	Genitourinary tract gonococcal infection
Urinary tract infections	10061182	Genitourinary tract infection
Urinary tract infections	10061395	Ureter abscess
Urinary tract infections	10062279	Urinary tract infection pseudomonal
Urinary tract infections	10062280	Urinary tract infection staphylococcal
Urinary tract infections	10064825	Urinary tract infection viral
Urinary tract infections	10064921	Urinary tract inflammation
Urinary tract infections	10065197	Cystitis viral
Urinary tract infections	10065198	Cystitis bacterial
Urinary tract infections	10065199	Cystitis helminthic
Urinary tract infections	10065213	Pyelonephritis viral
Urinary tract infections	10065214	Pyelonephritis fungal
Urinary tract infections	10065582	Urogenital infection fungal
Urinary tract infections	10065583	Urogenital infection bacterial
Urinary tract infections	10066757	Urinary tract abscess
Urinary tract infections	10068822	Emphysematous pyelonephritis
Urinary tract infections	10070300	Streptococcal urinary tract infection
Urinary tract infections	10074409	Escherichia pyelonephritis
Urinary tract infections	10075063	Urethritis mycoplasmal
Urinary tract infections	10078665	Bacterial urethritis
Urinary tract infections	10081163	Fungal urethritis
Urinary tract infections	10081262	Candida urethritis
Urinary tract infections	10082040	Nephritis bacterial
Volume depletion	10005697	Blood osmolarity increased
Volume depletion	10005731	Blood pressure ambulatory decreased
Volume depletion	10005734	Blood pressure decreased
Volume depletion	10005737	Blood pressure diastolic decreased
Volume depletion	10005748	Blood pressure immeasurable
Volume depletion	10005758	Blood pressure systolic decreased
Volume depletion	10005761	Blood pressure systolic inspiratory decreased
Volume depletion	10007979	Central venous pressure decreased
Volume depletion	10009192	Circulatory collapse
Volume depletion	10012174	Dehydration
Volume depletion	10013578	Dizziness postural

**Statistical Analysis Plan**

**Version: 3**

Lexicon Pharmaceuticals Protocol No. EFC14835

**Date of Issue: 19 February 2020**

Covance Study ID:000000154257

Volume depletion	10021097	Hypotension
Volume depletion	10021137	Hypovolaemia
Volume depletion	10021138	Hypovolaemic shock
Volume depletion	10026983	Mean arterial pressure decreased
Volume depletion	10031127	Orthostatic hypotension
Volume depletion	10036653	Presyncope
Volume depletion	10037327	Pulmonary arterial wedge pressure decreased
Volume depletion	10042772	Syncope
Volume depletion	10046640	Urine flow decreased
Volume depletion	10047235	Venous pressure decreased
Volume depletion	10047239	Venous pressure jugular decreased
Volume depletion	10047689	Volume blood decreased
Volume depletion	10050760	Blood urea nitrogen/creatinine ratio increased
Volume depletion	10050905	Decreased ventricular preload
Volume depletion	10053356	Blood pressure orthostatic decreased
Volume depletion	10059895	Urine output decreased
Volume depletion	10060089	Left ventricular end-diastolic pressure decreased
Volume depletion	10060231	Pulmonary arterial pressure decreased
Volume depletion	10063080	Postural orthostatic tachycardia syndrome
Volume depletion	10063927	Orthostatic intolerance
Volume depletion	10066077	Diastolic hypotension
Volume depletion	10069431	Orthostatic heart rate response increased
Volume depletion	10069583	Pulse volume decreased
Volume depletion	10072370	Prerenal failure
Pancreatitis	10033625	Pancreatic haemorrhage
Pancreatitis	10033635	Pancreatic pseudocyst
Pancreatitis	10033636	Pancreatic pseudocyst drainage
Pancreatitis	10033645	Pancreatitis
Pancreatitis	10033647	Pancreatitis acute
Pancreatitis	10033649	Pancreatitis chronic
Pancreatitis	10033650	Pancreatitis haemorrhagic
Pancreatitis	10033654	Pancreatitis necrotising
Pancreatitis	10033657	Pancreatitis relapsing
Pancreatitis	10048984	Pancreatic abscess
Pancreatitis	10052400	Oedematous pancreatitis
Pancreatitis	10056277	Pancreatorenal syndrome
Pancreatitis	10056975	Pancreatic phlegmon
Pancreatitis	10056976	Hereditary pancreatitis
Pancreatitis	10056977	Alcoholic pancreatitis
Pancreatitis	10058096	Pancreatic necrosis
Pancreatitis	10065189	Pancreatitis helminthic
Pancreatitis	10066127	Ischaemic pancreatitis

**Statistical Analysis Plan**

**Version: 3**

Lexicon Pharmaceuticals Protocol No. EFC14835

**Date of Issue: 19 February 2020**

Covance Study ID:000000154257

Pancreatitis	10069002	Autoimmune pancreatitis
Pancreatitis	10074894	Traumatic pancreatitis
Pancreatitis	10076058	Haemorrhagic necrotic pancreatitis
Venous thrombotic events	10003192	Arteriovenous fistula thrombosis
Venous thrombotic events	10003880	Axillary vein thrombosis
Venous thrombotic events	10006537	Budd-Chiari syndrome
Venous thrombotic events	10007830	Cavernous sinus thrombosis
Venous thrombotic events	10008138	Cerebral venous thrombosis
Venous thrombotic events	10014522	Embolism venous
Venous thrombotic events	10019713	Hepatic vein thrombosis
Venous thrombotic events	10023237	Jugular vein thrombosis
Venous thrombotic events	10027402	Mesenteric vein thrombosis
Venous thrombotic events	10034272	Pelvic venous thrombosis
Venous thrombotic events	10034324	Penile vein thrombosis
Venous thrombotic events	10036206	Portal vein thrombosis
Venous thrombotic events	10037377	Pulmonary embolism
Venous thrombotic events	10037421	Pulmonary microemboli
Venous thrombotic events	10037437	Pulmonary thrombosis
Venous thrombotic events	10037459	Pulmonary venous thrombosis
Venous thrombotic events	10038547	Renal vein embolism
Venous thrombotic events	10038548	Renal vein thrombosis
Venous thrombotic events	10038908	Retinal vein thrombosis
Venous thrombotic events	10041659	Splenic vein thrombosis
Venous thrombotic events	10042567	Superior sagittal sinus thrombosis
Venous thrombotic events	10043570	Thrombophlebitis
Venous thrombotic events	10043581	Thrombophlebitis migrans
Venous thrombotic events	10043595	Thrombophlebitis superficial
Venous thrombotic events	10043605	Thrombosed varicose vein
Venous thrombotic events	10044457	Transverse sinus thrombosis
Venous thrombotic events	10047193	Vena cava embolism
Venous thrombotic events	10047195	Vena cava thrombosis
Venous thrombotic events	10047249	Venous thrombosis
Venous thrombotic events	10048591	Post thrombotic syndrome
Venous thrombotic events	10049446	Subclavian vein thrombosis
Venous thrombotic events	10050216	Paget-Schroetter syndrome
Venous thrombotic events	10050902	Postoperative thrombosis
Venous thrombotic events	10051055	Deep vein thrombosis
Venous thrombotic events	10053182	Arteriovenous graft thrombosis
Venous thrombotic events	10061251	Intracranial venous sinus thrombosis
Venous thrombotic events	10061408	Venous thrombosis limb
Venous thrombotic events	10063363	Brachiocephalic vein thrombosis
Venous thrombotic events	10063909	Post procedural pulmonary embolism

**Statistical Analysis Plan**

**Version: 3**

Lexicon Pharmaceuticals Protocol No. EFC14835

**Date of Issue: 19 February 2020**

Covance Study ID:000000154257

Venous thrombotic events	10066881	Deep vein thrombosis postoperative
Venous thrombotic events	10067270	Thrombosis corpora cavernosa
Venous thrombotic events	10069909	Metastatic pulmonary embolism
Venous thrombotic events	10072059	Ovarian vein thrombosis
Venous thrombotic events	10074349	Ophthalmic vein thrombosis
Venous thrombotic events	10077623	Portosplenomesenteric venous thrombosis
Venous thrombotic events	10077829	Visceral venous thrombosis
Venous thrombotic events	10078810	Hepatic vein embolism
Thyroid cancer	10002240	Anaplastic thyroid cancer
Thyroid cancer	10016935	Follicular thyroid cancer
Thyroid cancer	10027105	Medullary thyroid cancer
Thyroid cancer	10033701	Papillary thyroid cancer
Thyroid cancer	10043744	Thyroid neoplasm
Thyroid cancer	10055107	Thyroid cancer metastatic
Thyroid cancer	10066136	Huerthle cell carcinoma
Thyroid cancer	10066474	Thyroid cancer
Thyroid cancer	10070567	Thyroid cancer stage 0
Thyroid cancer	10071027	Thyroid cancer stage I
Thyroid cancer	10071028	Thyroid cancer stage II
Thyroid cancer	10071029	Thyroid cancer stage III
Thyroid cancer	10071030	Thyroid cancer stage IV
Thyroid cancer	10072162	Thyroid cancer recurrent
Thyroid cancer	10072613	Thyroid B-cell lymphoma
Thyroid cancer	10073153	Familial medullary thyroid cancer
Thyroid cancer	10076603	Poorly differentiated thyroid carcinoma
Renal cell cancer	10038389	Renal cancer
Renal cell cancer	10038390	Renal cancer recurrent
Renal cell cancer	10038391	Renal cancer stage I
Renal cell cancer	10038392	Renal cancer stage II
Renal cell cancer	10038393	Renal cancer stage III
Renal cell cancer	10038394	Renal cancer stage IV
Renal cell cancer	10038410	Renal cell carcinoma recurrent
Renal cell cancer	10038411	Renal cell carcinoma stage I
Renal cell cancer	10038412	Renal cell carcinoma stage II
Renal cell cancer	10038413	Renal cell carcinoma stage III
Renal cell cancer	10038414	Renal cell carcinoma stage IV
Renal cell cancer	10050018	Renal cancer metastatic
Renal cell cancer	10050513	Metastatic renal cell carcinoma
Renal cell cancer	10061482	Renal neoplasm
Renal cell cancer	10067944	Hereditary leiomyomatosis renal cell carcinoma
Renal cell cancer	10067946	Renal cell carcinoma
Renal cell cancer	10073251	Clear cell renal cell carcinoma

Statistical Analysis Plan

Version: 3

Lexicon Pharmaceuticals Protocol No. EFC14835

Date of Issue: 19 February 2020

Covance Study ID:000000154257

Renal cell cancer	10078493	Papillary renal cell carcinoma
Pancreatic cancer	10018404	Glucagonoma
Pancreatic cancer	10022498	Insulinoma
Pancreatic cancer	10025997	Malignant neoplasm of islets of Langerhans
Pancreatic cancer	10029341	Neurotensinoma
Pancreatic cancer	10033609	Pancreatic carcinoma
Pancreatic cancer	10033610	Pancreatic carcinoma metastatic
Pancreatic cancer	10033613	Pancreatic carcinoma recurrent
Pancreatic cancer	10041329	Somatostatinoma
Pancreatic cancer	10047430	Vipoma
Pancreatic cancer	10051709	Gastrinoma malignant
Pancreatic cancer	10052747	Adenocarcinoma pancreas
Pancreatic cancer	10055006	Pancreatic sarcoma
Pancreatic cancer	10055007	Carcinoid tumour of the pancreas
Pancreatic cancer	10059320	Pancreatic carcinoma stage 0
Pancreatic cancer	10059321	Pancreatic carcinoma stage I
Pancreatic cancer	10059322	Pancreatic carcinoma stage II
Pancreatic cancer	10059323	Pancreatic carcinoma stage III
Pancreatic cancer	10059326	Pancreatic carcinoma stage IV
Pancreatic cancer	10061902	Pancreatic neoplasm
Pancreatic cancer	10067517	Pancreatic neuroendocrine tumour
Pancreatic cancer	10068909	Pancreatic neuroendocrine tumour metastatic
Pancreatic cancer	10069345	Solid pseudopapillary tumour of the pancreas
Pancreatic cancer	10073363	Acinar cell carcinoma of pancreas
Pancreatic cancer	10073364	Ductal adenocarcinoma of pancreas
Pancreatic cancer	10073365	Intraductal papillary-mucinous carcinoma of pancreas
Pancreatic cancer	10073367	Pancreatoblastoma
Bladder cancer	10004986	Bladder adenocarcinoma recurrent
Bladder cancer	10004987	Bladder adenocarcinoma stage 0
Bladder cancer	10004988	Bladder adenocarcinoma stage I
Bladder cancer	10004989	Bladder adenocarcinoma stage II
Bladder cancer	10004990	Bladder adenocarcinoma stage III
Bladder cancer	10004991	Bladder adenocarcinoma stage IV
Bladder cancer	10004992	Bladder adenocarcinoma stage unspecified
Bladder cancer	10005003	Bladder cancer
Bladder cancer	10005005	Bladder cancer recurrent
Bladder cancer	10005006	Bladder cancer stage 0, with cancer in situ
Bladder cancer	10005007	Bladder cancer stage 0, without cancer in situ
Bladder cancer	10005008	Bladder cancer stage I, with cancer in situ
Bladder cancer	10005009	Bladder cancer stage I, without cancer in situ
Bladder cancer	10005010	Bladder cancer stage II

Statistical Analysis Plan

Version: 3

Lexicon Pharmaceuticals Protocol No. EFC14835

Date of Issue: 19 February 2020

Covance Study ID:000000154257

Bladder cancer	10005011	Bladder cancer stage III
Bladder cancer	10005012	Bladder cancer stage IV
Bladder cancer	10005056	Bladder neoplasm
Bladder cancer	10005075	Bladder squamous cell carcinoma recurrent
Bladder cancer	10005076	Bladder squamous cell carcinoma stage 0
Bladder cancer	10005077	Bladder squamous cell carcinoma stage I
Bladder cancer	10005078	Bladder squamous cell carcinoma stage II
Bladder cancer	10005079	Bladder squamous cell carcinoma stage III
Bladder cancer	10005080	Bladder squamous cell carcinoma stage IV
Bladder cancer	10005081	Bladder squamous cell carcinoma stage unspecified
Bladder cancer	10005084	Bladder transitional cell carcinoma
Bladder cancer	10051690	Urinary bladder sarcoma
Bladder cancer	10057352	Metastatic carcinoma of the bladder
Bladder cancer	10066749	Bladder transitional cell carcinoma stage 0
Bladder cancer	10066750	Bladder transitional cell carcinoma recurrent
Bladder cancer	10066751	Bladder transitional cell carcinoma stage I
Bladder cancer	10066752	Bladder transitional cell carcinoma stage IV
Bladder cancer	10066753	Bladder transitional cell carcinoma stage II
Bladder cancer	10066754	Bladder transitional cell carcinoma stage III
Bladder cancer	10071664	Bladder transitional cell carcinoma metastatic
Bladder cancer	10078341	Neuroendocrine carcinoma of the bladder
Potentially leading to amputation	10003084	Areflexia
Potentially leading to amputation	10003178	Arterial thrombosis
Potentially leading to amputation	10003210	Arteriosclerosis
Potentially leading to amputation	10003222	Arteriosclerotic gangrene
Potentially leading to amputation	10006784	Burning sensation
Potentially leading to amputation	10007904	Cellulitis enterococcal
Potentially leading to amputation	10007905	Cellulitis gangrenous
Potentially leading to amputation	10007921	Cellulitis staphylococcal
Potentially leading to amputation	10007922	Cellulitis streptococcal
Potentially leading to amputation	10012174	Dehydration
Potentially leading to amputation	10012665	Diabetic gangrene
Potentially leading to amputation	10012679	Diabetic neuropathic ulcer
Potentially leading to amputation	10012680	Diabetic neuropathy
Potentially leading to amputation	10017711	Gangrene
Potentially leading to amputation	10020937	Hypoaesthesia
Potentially leading to amputation	10021137	Hypovolaemia
Potentially leading to amputation	10021519	Impaired healing
Potentially leading to amputation	10021784	Infected skin ulcer
Potentially leading to amputation	10022562	Intermittent claudication
Potentially leading to amputation	10024774	Localised infection
Potentially leading to amputation	10028862	Necrosis ischaemic
Potentially leading to amputation	10029331	Neuropathy peripheral

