10.3.1 Temporary treatment discontinuation with investigational medicinal product

Temporary treatment discontinuation may be considered by the Investigator because of suspected AEs. Lower extremity complications (such as skin ulcers, infection, osteomyelitis, and gangrene) requiring treatment should lead to temporary discontinuation of IMP. Reinitiating treatment with the IMP will be done under close and appropriate clinical/and or laboratory monitoring once the Investigator will have considered according to his/her best medical judgment that the occurrence of the concerned event was unlikely to be related to the IMP.

It is in the interest of the patient to monitor their blood glucose during the temporary discontinuation period, therefore regular determination of SMBG is to be performed and documented (see [Section 9.2.1.6](#)).

For all temporary treatment discontinuations, duration should be recorded by the Investigator in the appropriate pages of the e-CRF when considered as confirmed.

Temporary treatment discontinuation decided by the Investigator corresponds to more than 1 dose not administered to the patient.

Use of any different anti-hyperglycemic medication during the time of temporary treatment discontinuation (ie, insulin during a hospitalization) is recorded as concomitant medication with the name and doses recorded in the e-CRF.

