Diarrhea	Narrow search on "Noninfectious diarrhoea (SMQ)" [20000218] plus the following PTs (MedDRA v22.0): Gastroenteritis (10017888), Antidiarrhoeal supportive care (10055660), Enteritis (10014866), Enteritis leukopenic (10014877), Enterocolitis (10014893), Enterocolitis haemorrhagic (10014896)
Pancreatitis	PTs in Appendix B
Venous thrombotic events	PTs in Appendix B
Malignancies of special interest	Breast cancer: Narrow search on "Breast cancer: Narrow search on "Breast neoplasms, malignant and unspecified (SMQ)" [20000149] Prostate cancer: Narrow search on "Prostate neoplasms, malignant and unspecified (SMQ)" [20000152] Leydig-cell cancer: PTs of Leydig cell tumour of the testis (10024407) and Ovarian Sertoli-Leydig cell tumour (10073270) based on MedDRA v22.0 Thyroid cancer: PTs in Appendix B Renal cell cancer: PTs in Appendix B Pancreatic cancer: PTs in Appendix B Bladder cancer: PTs in Appendix B
EOSI AE leading to an amputation	
AE leading to an amputation	"AE Correction" as the reason for amputation in e-CRF "Other Procedures related to Amputation"
AE potentially leading to an amputation *	PTs in Appendix B

\* Search terms will be updated using the MedDRA version currently in effect at Covance at the time of database lock for EOSI identified by them.

\* AE potentially leading to an amputation: not belong to the EOSI list defined in protocol, the item is included and analyzed due to their relevance in regards to lower limb complications and amputations as a requirement from health authorities..

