#### **Analysis of Amputation**

The number (%) of patients with amputation will be summarized by treatment group and by PT and LLT during the study (ie, regardless of on- or post-treatment). Amputation is a procedure recorded in e-CRF “Other Procedures related to Amputation”. Patients who had a procedure related to amputation will be listed.

The number (%) of patients with an “AE leading to an amputation” will be summarized by treatment group and by PT. The “AE leading to an amputation” is determined by the AE identifier recorded in e-CRF “Other Procedures related to Amputation” when “AE correction” is chosen as the reason for the amputation procedure.

In addition, the number (%) of patients with an “AE potentially leading to an amputation” will be summarized by treatment group and by PT (as identified in [Table 3](#) in [Section 2.1.4.2](#); these PTs in [Table 3](#) were requested by the European Medicines Agency/ Pharmacovigilance Risk Assessment Committee[EMA/PRAC] Assessment Report 9 February 2017). Associated list will be provided as well, with patients who had an amputation procedure flagged. “AE potentially leading to an amputation” represents the condition that may potentially lead to the amputation procedure, but not in all cases an amputation has occurred (as per the EMA/PRAC request).

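### SAP Appendix B: the search list for AEs potentially leading to an amputation has four specific cellulitis terms but no unspecified one, so the supportive grouped count omits unspecified cellulitis

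*SAP*

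**What the plan says.** SAP Section 2.1.4.2, Table 3, gives the criterion for AEs potentially leading to an amputation as "PTs in Appendix B" and nothing else. A footnote to the table says that the item is outside the protocol's list of events of special interest and was added because health authorities required it.

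SAP Section 2.4.5.2, under Analysis of Amputation, plans the number and percentage of patients by treatment group and PT, with a listing. It explains that the group "represents the condition that may potentially lead to the amputation procedure", whether or not an amputation followed. It attributes the PTs to an EMA/PRAC assessment report of 9 February 2017.

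The cellulitis entries for this group in Appendix B are "Cellulitis enterococcal", "Cellulitis gangrenous", "Cellulitis staphylococcal" and "Cellulitis streptococcal".

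**The concern.** The search matches the coded PT. A limb cellulitis recorded without one of the three named organisms and without gangrene would, if coded to an unspecified term, match no cellulitis entry on the list. Whether cellulitis counts then depends on how it was worked up and described, as well as on whether it occurred.

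The group is meant to gather limb conditions that can precede amputation. Protocol Section 10.3.1 also treats infection as one of these conditions: it refers to "Lower extremity complications (such as skin ulcers, infection, osteomyelitis, and gangrene) requiring treatment". That sentence does not mention cellulitis, so it shows only that limb infection is of interest in this trial. At stake is the completeness of one grouped safety count in each arm.

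**Working it through.** No figure in the plan bears on this point, so the check is a reading of the list.

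**Step 1: read every row.** Appendix B has 97 terms labelled as potentially leading to amputation, in ascending code order and with no duplicate code.

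**Step 2: search for cellulitis.** Four terms contain the word:
- enterococcal (10007904)
- gangrenous (10007905)
- staphylococcal (10007921)
- streptococcal (10007922)

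There is no exact match for plain *Cellulitis*.

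**Step 3: rule out a lost row.** The row before the four is "Burning sensation" (10006784) and the row after is *Dehydration* (10012174). The run has no page header inside it and the codes stay in order. Nothing suggests that a row was lost when the file was read.

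**Step 4: compare with other conditions on the same list.**

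| Condition | Unspecified term listed? | Specific terms listed |
|---|---|---|
| Osteomyelitis | Yes (10031252) | acute, chronic, salmonella, staphylococcal, bacterial, fungal |
| Wound infection | Yes (10048038) | staphylococcal, pseudomonas, bacterial, fungal, postoperative |
| Gangrene | Yes (10017711) | diabetic, arteriosclerotic, dry |
| Cellulitis | No | enterococcal, gangrenous, staphylococcal, streptococcal |
| Abscess | No | limb, subcutaneous, wound, bone, subperiosteal |
| Necrosis | No | ischaemic, wound, extremity |

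The first three rows show the pattern that cellulitis does not follow. The last two show that the pattern is not universal.

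**Step 5: ask whether a narrow search was intended.** The list also takes in *Burning sensation*, *Paraesthesia*, *Dehydration*, *Hypovolaemia*, *Wound* and *Localised infection*. A wish to restrict the search to specific limb disease does not explain the absence of unspecified cellulitis.

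**Step 6: ask whether a broader listed term would catch the event.** *Skin infection*, *Soft tissue infection*, *Localised infection* and *Diabetic foot infection* are listed, but they catch only events coded to them.

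**Effect of adding the term.** The list would go from 97 to 97 + 1 = 98 terms, and the cellulitis terms from 4 to 4 + 1 = 5. The change in patient counts cannot be computed, because neither document gives a rate.

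**The case against.** The strongest objection is that the list is not the sponsor's own. If the EMA/PRAC request omits unspecified cellulitis, Appendix B is a faithful copy. That source is not in the documents, so this stands: a transcription error cannot be asserted. Nor do the documents show that MedDRA v22.0 has an unspecified cellulitis PT, so that needs a look-up.

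The second objection is that the pattern is selective, since plain abscess and necrosis are missing too. This also stands. The comparison makes an oversight plausible but does not prove one.

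The third concerns consequence. A reader might infer that these events are lost, or that an excess on sotagliflozin could be hidden. The documents do not support either:
- SAP Section 2.4.5.2 tabulates all treatment-emergent AEs by arm and PT and lists all AEs, so an imbalance in cellulitis would still be visible there.
- Amputation procedures, and the AEs recorded as their reason, come from a dedicated e-CRF page and do not depend on this list.
- A blinded committee reviews amputation cases and reports to the DMC (Protocol Section 6.4.4).
- The safety analysis is descriptive, and the same list applies to both arms.

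A reader might also want a number. Assuming that 1% to 3% of 500 patients have such an event gives 0.01 × 500 = 5 to 0.03 × 500 = 15 patients. The rate is only an assumption. Even then, 5 to 15 would be an upper limit on the change in the group total, because a patient with another listed term is already counted.

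On the other side, the planned MedDRA update at database lock (footnote to Table 3) does not clearly close the gap. It is a version update and does not promise a completeness check. SAP Table 2 records that the PT lists were already updated in version 2, and version 3 still lacks the term.

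**Conclusion.** The point holds as a gap in one supportive summary. As written, an event coded to unspecified cellulitis is left out of the grouped table and its listing, while loosely related terms such as *Wound* and *Burning sensation* are counted. This assumes that the unspecified PT exists in the MedDRA version used and that the list is applied as printed.

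The size of the undercount is unknown and cannot be derived from the documents. The origin of the gap is also open: it may lie in the EMA/PRAC request or in its transcription. No efficacy estimate, test or amputation count changes. The point ranks as a worthwhile improvement and does not threaten the trial's conclusions.

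**What to change.** Check the cellulitis entries in SAP Appendix B against the EMA/PRAC request, and confirm the unspecified PT in the MedDRA version in use at database lock. Then:
- If the term was dropped in transcription, add it to Appendix B.
- If the request itself omits it, keep the requested list as the main row. Add a supplementary row that includes unspecified cellulitis, and state that the difference is deliberate.

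The cost is one dictionary look-up, one comparison with the source and one extra line or row, best settled before unblinding. The downside is that some non-limb cellulitis will be counted. That already happens with the four listed cellulitis terms and *Skin infection*, none of which specifies a limb.
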